3.3.2 Safety Outcome Measures (Part 1; OLE)

The safety outcome measures for Part 1 of this study are as follows:

- Incidence and severity of adverse events
- Incidence of serious adverse events
- Incidence and severity of infection-related adverse events
- Incidence of serious infection-related adverse events
- Incidence and severity of injection-site reactions
- Incidence of adverse events leading to etrolizumab discontinuation
- Incidence of laboratory abnormalities
- Incidence of malignancies
- Incidence of ATAs to etrolizumab
- Incidence and severity of hypersensitivity reaction events

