5.3.2 Serious Adverse Events (Immediately Reportable to the Sponsor)

All serious adverse events are required to be reported by the investigator to the Sponsor immediately (i.e., no more than 24 hours after learning of the event; see Section 5.5.2 for reporting instructions). A serious adverse event is any adverse event that meets any of the following criteria:

- Fatal (i.e., the adverse event actually causes or leads to death)
- Life threatening (i.e., the adverse event, in the view of the investigator, places the patient at immediate risk of death)
 - This does not include any adverse event that had it occurred in a more severe form or was allowed to continue might have caused death.
- Requires or prolongs inpatient hospitalization (see Section 5.4.6.10)
- Results in persistent or significant disability/incapacity (i.e., the adverse event results in substantial disruption of the patient's ability to conduct normal life functions)
- Congenital anomaly/birth defect in a neonate/infant born to a mother exposed to study drug
- Significant medical event in the investigator's judgment (e.g., may jeopardize the patient or may require medical/surgical intervention to prevent one of the outcomes listed above)

The terms "severe" and "serious" are not synonymous. Severity refers to the intensity of an adverse event (rated as mild, moderate, or severe or according to National Cancer Institute Common Terminology Criteria for Adverse Events [NCI CTCAE] criteria; see Section 5.4.4); the event itself may be of relatively minor medical significance (such as severe headache without any further findings).

Severity and seriousness need to be independently assessed for each adverse event recorded on the eCRF.

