5.4 METHODS AND TIMING FOR CAPTURING AND ASSESSING SAFETY PARAMETERS

5.4.1 Adverse Event Reporting Period for Part 1 (OLE)

After informed consent has been obtained, all adverse events, regardless of relationship to study drug, will be reported until the patient completes Part 1 (OLE).

During Part 1 (OLE), the investigator is responsible for ensuring that all adverse events (see Section 5.3.1 for definition) are recorded on the Adverse Event eCRF and reported to the Sponsor in accordance with instructions provided in this section and in Sections 5.5, 5.6, and 5.7. The investigator is also responsible for reporting medical device complaints (see Section 4.3.3.3).

For each adverse event recorded on the Adverse Event eCRF, the investigator will make an assessment of seriousness (see Section 5.3.2 for seriousness criteria), severity (see Section 5.4.4), and causality (see Section 5.4.5).

Investigators will seek information on adverse events at each patient contact. All adverse events, whether reported by the patient or noted by study personnel, will be recorded in the patient's medical record and on the Adverse Event eCRF. Past resolved adverse events will be recorded in the medical history according to their medical relevance. Adverse events reported ongoing at the end of the Phase II OLE or Phase III controlled studies will be stated unresolved in those studies and reopened in Study GA28951. The adverse event will be reported in Study GA28951 with the start date and adverse event term identical to those in the parent study (i.e., the Phase II OLE study or a Phase III controlled study). The severity (NCI CTCAE grade) should be evaluated by the investigator at the start of Part I (OLE) and recorded in the "AE initial NCI CTCAE grade" field of the Adverse Event eCRF for Study GA28951. The most extreme NCI CTCAE grade for the event should also be recorded, taking into account the severity of the event since it was first reported during the parent study.

Adverse events reported as ongoing at the end of Part 1 (OLE) (i.e., the end of the 12-week safety follow-up) will be recorded as unresolved.

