5.4.6.3 Persistent or Recurrent Adverse Events

A persistent adverse event is one that extends continuously, without resolution, between patient evaluation timepoints. Such events should only be recorded once on the Adverse Event eCRF. The initial severity (NCI CTCAE grade) of the event should be recorded at the time the event is first reported during Study GA28951. If a persistent adverse event becomes more severe, the most extreme NCI CTCAE grade should also be recorded on the Adverse Event eCRF. For adverse events reported as ongoing at the end of a parent study (i.e., the Phase II OLE study or a Phase III controlled study), the severity (NCI CTCAE grade) should be evaluated by the investigator at the start of Part 1 (OLE) and recorded in the "AE initial NCI CTCAE grade" field of the Adverse Event eCRF for Study GA28951. The most extreme NCI CTCAE grade for the event should also be recorded, taking into account the severity of the event since it was first reported during the parent study.

If the event becomes serious, it should be reported to the Sponsor immediately (i.e., no more than 24 hours after learning that the event became serious; see Section 5.5.2 reporting instructions). The Adverse Event eCRF should be updated by changing the event from "non-serious" to "serious," providing the date that the event became serious, and completing all data fields related to serious adverse events.

A recurrent adverse event is one that resolves between patient evaluation timepoints and subsequently recurs. Each recurrence of an adverse event should be recorded separately on the Adverse Event eCRF.

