Summary tables will be generated for AEs, serious adverse events (SAEs), deaths, AEs leading to discontinuation of study drug, and AESIs. A listing will be generated for AEs, deaths, selected AESIs/specific AEs, and COVID-19 AEs. Pregnancies will be reported as narratives in the study CSR.

Summary tables of AEs will summarize the incidence of treatment-emergent AEs only. Treatment-emergent events are defined as any new AE reported on or after the first dose of OLE study drug or any worsening of an existing condition. Note that worsening of existing conditions include AEs ongoing from the UC parent studies (GA28948, GA28949, GA28950, GA29102, and GA29103). Otherwise, only AEs reported on or after the first dose of OLE study drug are included. If the onset date of the AE is prior to

the day of first dose, the AE will be considered treatment emergent only if the most extreme intensity is greater than the initial intensity (i.e., the intensity for a given AE increases and its end date is on or after the date of the first dose). For all summary tables, the AEs will be sorted by SOC (in decreasing order of overall incidence) and then by preferred term (PT) (in decreasing order of overall incidence).

For OLE etrolizumab treatment, the incidence count for each AE PT will be defined as the number of patients reporting at least one treatment-emergent occurrence of the event (multiple occurrences of the same AE in 1 patient will be counted only once). The proportion of patients with an AE will be calculated as the incidence count divided by the total number of patients in the population. Each table will also present the total number of AEs reported where multiple occurrences of the same AE in an individual are counted separately.

Rate tables will be generated for selected AEs of interest. The rate per 100 patient years and 95% CIs will be summarized by treatment group and will be calculated by:

$$\begin{aligned} & \text{AE Rate (per 100 patient years)} \\ &= \frac{\text{Total number of AEs (in OLE only)}}{\text{Total number of patient years at risk (in OLE only)}} \times 100 \end{aligned}$$

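### A carried-over adverse event that turns serious or stops etrolizumab in the OLE is left out of the SAE or discontinuation table if its recorded most extreme grade equals its OLE-entry grade

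*SAP*

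**What the plan says.** SAP 4.2.2 sets out the outputs: "Summary tables will be generated for AEs, serious adverse events (SAEs), deaths, AEs leading to discontinuation of study drug, and AESIs". It then restricts them: "Summary tables of AEs will summarize the incidence of treatment-emergent AEs only". The incidence count for a preferred term is "the number of patients reporting at least one treatment-emergent occurrence of the event". The section first defines treatment emergence widely, so that worsening of an existing condition qualifies. It then gives an operational rule for onset before the first OLE dose: "the AE will be considered treatment emergent only if the most extreme intensity is greater than the initial intensity". The parenthesis after that restates the rule as a grade increase in an event that had not ended before the first dose. Seriousness and action taken with study drug are not mentioned.

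The protocol determines what the record of a carried-over event contains:

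- Section 5.4.1, on onset: "The adverse event will be reported in Study GA28951 with the start date and adverse event term identical to those in the parent study".
- Sections 5.4.1 and 5.4.6.3, on grade: the initial grade is the one assessed at the start of Part 1. The most extreme grade is the highest since the event was first reported in the parent study.
- Section 5.4.6.3, on seriousness: a persistent event has one record. If it becomes serious, that record is updated, "providing the date that the event became serious, and completing all data fields related to serious adverse events".
- Section 5.3.2: "Severity and seriousness need to be independently assessed for each adverse event recorded on the eCRF".

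Protocol 3.3.2 and SAP 1.3.2 both list the incidence of serious adverse events and "Incidence of adverse events leading to etrolizumab discontinuation" as Part 1 safety outcomes.

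**The concern.** A test on grade alone decides whether a carried-over event can enter tables that are not about grade. The protocol treats severity and seriousness as separate assessments, so an unchanged grade does not mean that nothing new happened in the OLE. The event may have put the patient in hospital, or may be the reason that etrolizumab was stopped.

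Carried-over events related to ulcerative colitis are plausible here. Protocol Table 1 lets patients enter after relapse, disease worsening or rescue medication, and Protocol 5.4.6.9 has unexpected worsening of colitis recorded as an adverse event.

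At stake is the completeness of two named safety outcomes in a study whose purpose is long-term safety. Two outputs of the same report could also disagree: a stop attributed to a carried-over event would be counted among the discontinuation reasons under SAP 4.1.1 but be absent from the adverse event discontinuation table under SAP 4.2.2.

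**Working it through.** The plan gives no figure on this point, so there is none to reproduce. The check applies the SAP rule to the record fields as the protocol defines them.

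**Inputs.** For an event still ongoing at the first OLE dose, let P be the highest grade in the parent study, S the grade at OLE start and O the highest grade in the OLE (P ≥ S, O ≥ S). By Protocol 5.4.1, the initial grade is S and the most extreme grade is max(P, O).

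**Rule (SAP 4.2.2).** Treatment emergent if max(P, O) > S.

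**Example records**

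| Record | P / S / O | What happens in the OLE | max(P, O) > S? | Result |
|---|---|---|---|---|
| A | 2 / 2 / 2 | Etrolizumab stopped for the event | 2 > 2, no | Not in discontinuation table |
| B | 3 / 3 / 3 | Becomes serious | 3 > 3, no | Not in SAE table |
| C | 3 / 1 / 1 | Etrolizumab stopped for the event | 3 > 1, yes | Counted |

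If record A had begun after the first OLE dose, it would be counted whatever its grade.

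**All grade patterns.** Take S from 1 to 4, P from S to 4 and O from S to 5.

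- Total: 4×5 + 3×4 + 2×3 + 1×2 = 40.
- No grade rise in the OLE (O = S): 4 + 3 + 2 + 1 = 10.
- Of these 10, the rule excludes the 4 with P = S = O: 1/1/1, 2/2/2, 3/3/3 and 4/4/4.
- The other 10 − 4 = 6 have P > S and pass, because the parent-study peak counts towards the most extreme grade.

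These are counts of patterns, not expected frequencies.

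**Which tables are exposed.** The discontinuation gap can arise at any of the four excluded grades. The became-serious gap is mainly at Grades 1 to 3, because Protocol Table 3 (footnote d) already requires Grade 4 events to be reported as serious. A fatal event reaches Grade 5 and normally passes the test, so the deaths table is little affected.

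**Does anything restore the excluded events?** Nothing in either document does.

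- Protocol 6.3.1 lists the SAE, death and discontinuation summaries without an explicit treatment-emergent limit, but SAP Section 1 says that the SAP supersedes the protocol for reporting.
- SAP 4.2.4 refers only to flagging events in a manner similar to treatment emergence.
- The rate tables in SAP 4.2.2 exclude every event with onset before the first dose, whatever its grade.

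**The case against.** The strongest reply is that the gap is narrow and partly covered elsewhere. Much of that stands.

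- **Scope.** A reader might infer that every carried-over event that turns serious or stops treatment without a grade rise in the OLE is lost. The documents do not support this. The most extreme grade includes the parent-study period, so an event that had eased by OLE entry passes the test.
- **Other outputs.** The reasons for stopping treatment are listed and summarized under SAP 4.1.1, independently of the treatment-emergent flag. The adverse event listing in SAP 4.2.2 is not stated to be limited to treatment-emergent events. The events leave particular tables, not the data. A listing gives no incidence, however, and SAP 4.2.2 names no separate SAE or discontinuation listing.
- **Plausibility.** Each recurrence gets a new record and hence a new onset (Protocol 5.4.6.3). The exclusions in Protocol 4.1.2 also keep out some patients with serious ongoing conditions. An affected event must be continuous and recorded at one grade throughout. That limits the number but does not remove the gap.
- **Consequence.** The study is single-arm and descriptive, without tests, and is reported in a synoptic report after Part 1 was terminated. No decision threshold rests on these counts.
- **Reading of the restriction.** The SAP does not repeat the treatment-emergent limit separately for the SAE and discontinuation tables. It does not exempt them either, and its counting rule is framed in treatment-emergent occurrences. If an exemption is intended, the SAP should say so.

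**Conclusion.** The point holds for carried-over events whose recorded initial and most extreme grades are equal. If such an event becomes serious or leads to stopping etrolizumab in the OLE, SAP 4.2.2 as written omits it from the SAE or discontinuation table. This rests on reading the treatment-emergent restriction as covering those tables, which is the natural reading of the section.

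The size cannot be computed. It would need the number of carried-over events, the share with equal grades, and the share of those that turn serious or cause a stop. The documents give none of these.

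A reader might also infer that the rule makes long-term tolerability look better overall. That does not follow. The same rule admits carried-over events that peaked in the parent study and never worsened in the OLE, so the net direction for the overall adverse event table is unknown. What is shown is the omission of specific events from two named safety outcomes. That is worth correcting because the correction is cheap.

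**What to change.** Add to SAP 4.2.2 that, regardless of grade change:

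- the SAE table includes any carried-over event whose became-serious date is on or after the first OLE dose;
- the discontinuation table includes any carried-over event recorded as leading to etrolizumab discontinuation in the OLE.

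The became-serious date is already collected under Protocol 5.4.6.3. For stops, Protocol 4.5.1.1 records a primary reason but does not say that it is tied to a particular adverse event record. The planned discontinuation table needs that link for every event it counts, so no new requirement arises.

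The change should not rest on a general re-test of whether grade rose above the OLE-entry grade during the OLE. The fields described hold the entry grade and a most extreme grade that spans the parent study, and these cannot separate a parent-study peak from an OLE peak.

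The cost is one sentence in the SAP and a small programming change. The reported SAE and discontinuation percentages may come out slightly higher.

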5.1.1.2 Hypersensitivity Reactions Background

In completed Phase I/II clinical trials of etrolizumab, one serious adverse event of hypersensitivity (Grade 2) has been reported. No anaphylactic, anaphylactoid, or severe hypersensitivity reactions were observed; however, anaphylaxis and hypersensitivity reactions will be closely monitored during the study.

Patient Selection

Patients who developed an anaphylactic/anaphylactoid or severe allergic reaction to study medication during the Phase II OLE or Phase III studies will be excluded from participation in Part 1 of this study.

Education, Monitoring, and Management

The first four injections should be administered in the clinic in order to monitor for any possible hypersensitivity reactions, given that patients who received blinded placebo in the randomized studies may receive their first active etrolizumab dose upon enrolling in the OLE-SM study. After each of these four injections, the patient must be monitored for 60 minutes. Epinephrine must be readily available for immediate use if required to treat

anaphylaxis. Adjunctive medications such as parenteral diphenhydramine and inhaled bronchodilators may be used IN ADDITION to epinephrine if necessary. Resuscitation equipment should also be available. Site personnel must be able to detect and treat such reactions.

Patients should be instructed to recognize the symptoms of any anaphylactic, anaphylactoid, or hypersensitivity reaction and to contact a HCP or seek immediate care in case of any such symptoms. Patients are to be provided with alert cards to remind them and a caregiver or partner of the above.

If the patient develops any systemic hypersensitivity or anaphylactic or anaphylactoid reaction, the event should be expeditiously reported to the Sponsor as an adverse event of special interest or serious adverse event, as appropriate, within 24 hours.

If a patient has symptoms of anaphylaxis or severe hypersensitivity, the administration of etrolizumab must be discontinued permanently.

Refer to [Appendix 9](#) (Clinical Criteria for Diagnosis Anaphylaxis).

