6.3.1 Adverse Events

Verbatim descriptions of treatment-emergent adverse events will be coded and their incidence and observation time-adjusted rate will be summarized, as appropriate. A treatment-emergent adverse event is defined as any new adverse event reported or any worsening of an existing condition on or after the first dose of study drug. In addition, separate summaries will be generated for serious adverse events, deaths, and adverse events leading to discontinuation of etrolizumab. Adverse events will be summarized by mapped term, appropriate thesaurus level, and toxicity grade.

Analyses will be performed for:

- Systemic hypersensitivity events
Specific analyses will be performed for anaphylactic reactions with use of the anaphylactic reaction Sampson's criteria (see [Appendix 9](#)).
- Serious infections, in particular GI infections
- Opportunistic infections
- Malignancies
- Injection-site reactions

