1.3 OUTCOME MEASURES FOR GA28951 PART 1 (OLE)

1.3.1 Efficacy Outcome Measures

The efficacy outcome measures for this study are as follows:

- pMCS remission assessed at Weeks 0, 4, 8 and then in 12-week intervals during GA28951 Part 1 (OLE)
- MCS remission assessed at Week 108 during GA28951 Part 1 (OLE)
- Endoscopic remission at Week 108 during GA28951 Part 1 (OLE)

The efficacy outcome definitions are provided below:

Outcome Measure	Definition
Mayo Clinic Score (MCS)	MCS (0–12) is a composite of 4 assessments, each rated from 0-3: stool frequency, rectal bleeding, endoscopy, and PGA
Partial Mayo Clinic Score (pMCS)	pMCS (0–9) is a composite of 3 assessments, each rated from 0-3: stool frequency, rectal bleeding, and PGA

MCS Remission	MCS ≤ 2 with individual subscores ≤ 1 and a rectal bleeding subscore of 0
MCS Clinical Response	MCS with ≥ 3 -point decrease and 30% reduction from baseline as well as ≥ 1 -point decrease in rectal bleeding subscore or an absolute rectal bleeding score of 0 or 1
pMCS Remission	pMCS ≤ 2 , with, rectal bleeding score of 0, PGA 0–1 and stool frequency subscore 0–1
Improvement in endoscopic appearance of the mucosa	Endoscopy subscore ≤ 1
Endoscopic Remission	Endoscopy subscore = 0

ES= Endoscopic Subscore; PGA = Physician's Global Assessment.

Endoscopy Score=1 includes mild friability criteria unless identified in the description of an endpoint above.

1.3.2 **Safety Outcome Measures**

The safety outcome measures for GA28951 Part 1 (OLE) of this study are as follows:

- Incidence and severity of adverse events
- Incidence of serious adverse events
- Incidence, rate per subject-year, and severity of infection-related adverse events
- Incidence of serious infection-related adverse events
- Incidence and severity of injection-site reactions
- Incidence of adverse events leading to etrolizumab discontinuation
- Incidence of laboratory abnormalities
- Incidence and rate per subject-year of malignancies
- Incidence and severity of hypersensitivity reactions

1.3.3 **Exploratory Outcome Measures**

The exploratory outcome measures for GA28951 Part 1 (OLE) are as follows:

- Histologic appearance of mucosa at Week 108
- Incidence of ATAs to etrolizumab (*de-prioritised from a safety outcome measure. See Section 4.4 for details*)

Due to termination of study GA28951, exploratory outcome measures will **not** be reported in the Primary CSR.

1.4 **ANALYSIS TIMING**

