4.1 GENERAL CONSIDERATIONS

4.1.1 Analysis of Study Conduct

The number of patients who enrolled in Part 1 (OLE) and Part 2 (SM) will be tabulated. The number of patients who discontinued early (early discontinuation of OLE treatment or early termination from the study) or completed the study will be tabulated.

Reasons for early discontinuation of treatment or early termination from the study will be listed and summarized. Any eligibility criteria exceptions and other major protocol deviations will also be summarized. The data will also be summarized by origin of the patient (i.e., by original Phase II OLE protocol or Phase III controlled protocol).

Since Part 1 (OLE) of GA28951 was terminated by the Sponsor on 15th February 2022, no patients are expected to reach treatment completion. As a result of this, the end of Part 1 (OLE) of GA28951 is defined from the last dose date in GA28951 on 15th May 2022.

In summary, the following will be summarized for GA28951 Part 1 (OLE):

- Analysis populations
- Patient disposition
- Study treatment completion/discontinuation
- Study completion/discontinuation
- Major protocol deviations
- Exposure

Treatment Labels

For the OLE population, the only treatment arm to be summarized is:

Group	Patients Included
OLE Etrolizumab	Patients in the OLE population who receive at least one dose of etrolizumab in Study GA28951 Part 1 (OLE)

OLE = Open-Label-Extension

Part 1 (OLE) Day 1

OLE Study Day 1 is defined as the day patient has the first receipt of study drug in GA28951 Part 1 (OLE).

Baseline

For patients who were previously enrolled in one of the Phase III studies, baseline is defined as the last available assessment prior to first receipt of study drug in the Induction Phase of the parent studies: GA28948, GA28949, GA28950, GA29102, and GA29103.

For patients who were previously enrolled in the Phase II trial GA27927, baseline is defined as the last available assessment prior to first receipt of study drug in their parent trial ABS4986g.

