where the total patient-years at risk is the sum over all patients of the time intervals (in years) from the first dose of study treatment in Part 1 (OLE) until the patient completes/withdraws from the study (including the 12-week safety follow-up, if applicable). Only treatment emergent AEs with an onset date after the first dose of open label etrolizumab in GA28951 will be included within these outputs.

All summary tables and listings will report AEs using the OLE population.

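### The adverse event rate tables ask for an onset date after the first OLE dose, while treatment-emergent events are defined as on or after it; read literally, Day 1 events leave the rate numerator

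*SAP*

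**What the plan says.** SAP 4.2.2 contains three rules that bear on an event dated on the day of the first open-label dose.

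- **Treatment-emergent definition.** A new event qualifies if it is "any new AE reported on or after the first dose of OLE study drug". Protocol 6.3.1 uses the same boundary: "any new adverse event reported or any worsening of an existing condition on or after the first dose of study drug". It plans both incidence and observation-time-adjusted rates for that set, as appropriate.
- **Rate-table filter.** A further restriction applies to the rate tables: "Only treatment emergent AEs with an onset date after the first dose of open label etrolizumab in GA28951 will be included within these outputs".
- **Rate denominator.** Patient-years at risk start at each patient's first dose in Part 1 and run to completion or withdrawal, including safety follow-up where applicable.

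SAP 4.1.1 makes OLE Day 1 the calendar day on which study drug is first received. The scope of the rate tables is left open: "Rate tables will be generated for selected AEs of interest". Among the safety outcomes in SAP 1.3.2, a rate is named for infections ("Incidence, rate per subject-year, and severity of infection-related adverse events") and for malignancies. Hypersensitivity and injection-site reactions have incidence and severity only.

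**The concern.** The filter compares an onset *date* with the first dose and drops the words *on or*. Under a plain date comparison, a reaction half an hour after the first injection carries the Day 1 date and is therefore not later than Day 1. It would be treatment-emergent and counted in the incidence tables, yet absent from the rate numerator, while the patient's Day 1 time stayed in the denominator.

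First-dose reactions are of particular interest in this trial. Protocol 5.1.1.2 explains in-clinic dosing by noting that patients previously on blinded placebo "may receive their first active etrolizumab dose upon enrolling in the OLE-SM study". Protocol 5.4.6.1 covers local reactions during or within 24 hours of an injection, so those following the first dose can readily carry the Day 1 date. If such reactions are tabulated as rates, the literal rule can only lower those rates.

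**Working it through.** **Step 1: trace a new event dated on OLE Day 1 through the rules.**

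| Rule | Wording of the boundary | Day 1 event |
|---|---|---|
| Treatment-emergent (SAP 4.2.2, Protocol 6.3.1) | on or after first dose | counted |
| Incidence tables and AE listing (SAP 4.2.2) | tables use the treatment-emergent set; listing covers AEs | counted |
| Rate numerator (SAP 4.2.2) | onset date after first dose | dropped if read as a date comparison |
| Rate denominator (SAP 4.2.2) | from first dose | Day 1 time counted |

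The conflict is therefore confined to the rate numerator. No passage states that the onset time of an adverse event is recorded, so nothing in the documents secures a clock-time reading.

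**Step 2: size of the denominator part.** With the maximum of about 2100 patients (SAP 2.2), Day 1 contributes 2100 / 365.25 = 5.75 patient-years. As a share of all patient-years this is 1 / (365.25 × T), where T is mean follow-up in years. The documents do not give T. For T = 1 the share is 0.27%; for T = 4 it is 0.07%. This is negligible.

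**Step 3: infections and malignancies.** If onsets are spread evenly over follow-up (an assumption), the share falling on Day 1 equals the share of time falling on Day 1. The rate would be understated by the same 0.07% to 0.27%, which is near zero.

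**Step 4: acute reactions, if they are chosen for rate tables.** The SAP formula is rate = 100 × events / patient-years. With q Day 1 events per patient, the literal rule removes 100 × q × N / (N × T) = 100 × q / T events per 100 patient-years. Neither q nor T is in the documents. The table shows only how the formula behaves under assumed values.

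| Assumed q | T = 1 | T = 2 | T = 4 |
|---|---|---|---|
| 0.1% | 0.10 | 0.05 | 0.025 |
| 1% | 1.0 | 0.5 | 0.25 |
| 5% | 5.0 | 2.5 | 1.25 |

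The proportional understatement equals the share of all counted events that start on Day 1. That share is also unknown.

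The SAP states no rate for this point, so there is no planned figure to reproduce.

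**The case against.** The strongest reply is that the sentence has a different purpose. SAP 4.2.2 counts worsened parent-study events as treatment-emergent although they began before the OLE. The rate formula is restricted to OLE events, and the filter removes those earlier onsets. SAP Section 3 (Table 2) and SAP 4.2.4 both open the reporting period at the first dose and then speak loosely of events after it. SAP 4.2.4 adds that flagging should resemble treatment-emergent flagging. The filter also says after the first dose, not after its date, and a reaction to the first injection is after that injection in the ordinary sense. This stands as the probable intent. It does not settle the programming, because the rule is written on onset date and the same section says *on or after* where it means to include the day.

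Several stronger readings are tempting, but the documents do not support them.

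- *The reported rates are biased.* This follows only if the literal reading is programmed and acute reactions are selected for rate tables. Neither is established. Listing hypersensitivity first among the events of special interest does not place it in a rate table; SAP 4.2.2 promises summary tables for those events.
- *The understatement is some substantial percentage, such as 10% to 50%.* No document gives the Day 1 share. The numerator counts every occurrence over repeated 4-weekly dosing, and the 60-minute observation follows each of the first four injections, so it does not single out Day 1.
- *This wording is why incidence and rate tables fail to reconcile.* They would differ anyway: incidence counts a patient once per term and includes worsened parent-study events, whereas rates count every occurrence and exclude those events.
- *A safety signal would be lost.* Day 1 events remain in the incidence tables, in the total event counts shown with them and in the listing.

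**Conclusion.** The wording conflict is real and minor. Followed literally, the rate-table filter drops new Day 1 events that the treatment-emergent definition keeps, and the error can go in one direction only. For the two outcomes with a named rate it is near zero, on the assumption of evenly spread onsets. For hypersensitivity or injection-site reactions it would lower the rate by an amount that cannot be estimated from the documents, and only if these are among the selected events. The denominator contribution is trivial. The study is single-arm and descriptive, so no test or treatment comparison depends on the answer. The case for changing the text is that two programmers could reasonably build different tables from it.

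**What to change.** In SAP 4.2.2, reword the rate-table filter to require an *onset date on or after the date of the first dose of open-label etrolizumab in GA28951*. This still excludes parent-study events that began before that date, which appears to be the purpose of the sentence. State that Day 1 onsets are counted in the rate tables in the same way as for incidence, so that no onset time is needed. The cost is one phrase in the SAP and, if the literal rule has been programmed, one comparison in the rate-table code. No new data are required, and the incidence tables and listings do not change.
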